#### 6.6.1.2.3. Follow-up TEAEs

Follow-up TEAEs will be summarized by SOC and PT for safety analysis set by treatment group for the following:

- TEAEs
- TEAEs by severity (total, mild, moderate, severe, not reported)
- SAEs.

### 6.6.1.3. Other Significant AEs

All-cause (for on-treatment period and follow-up period) and treatment-related (for on-treatment period) AEs will be generated separately for other significant AEs, which will be summarized by SOC and PT for the safety analysis set by treatment group:

- Hepatic-related AEs
- Cardiovascular AEs
- Suicidality AEs
- Local irritation AEs
- Potential drug abuse AEs
- Hypertension AEs
- Raynaud's phenomenon AEs

Potential drug abuse AEs will be displayed in alphabetical order by severity and PT without SOC.

Definitions of the above AEs are described in the following and [Appendix 3.1](#), and are subject to change due to sponsor internal update; minor updates to the definitions will be included in the programming A&R plan before study database lock.

#### Hepatic-Related AEs

Hepatic-related AE PTs will include the following:

- “Hepatic disorders” SMQ: All PTs except those in “Congenital, familial, neonatal and genetic disorders of the liver” SMQ.

#### Potential Drug Abuse AEs

Potential drug abuse AE PTs will include any of the following:

- “Drug abuse, dependence and withdrawal” SMQ: All PTs
- PTs in [Table 3 \(Appendix 3.1\)](#). This list is based on clinical review of AE PTs in the depressant, stimulant, and psychotomimetic categories of the General disorders and administration site conditions SOC, Nervous system disorders SOC, and Psychiatric disorders SOC, as recommended in FDA Guidance for Industry Assessment of Abuse Potential of Drugs Section V.B (January 2017). Note that some PTs in this list are also part of the “Drug abuse, dependence and withdrawal” SMQ.

- PT of dizziness only if concurrent with any euphoria-related AE in [Table 4 \(Appendix 3.1\)](#), which is a subset of PTs in [Table 3 \(Appendix 3.1\)](#).
  - For a given safety analysis period, AEs are considered concurrent if (1) their durations overlap, and (2) their AE start dates are in the same safety analysis period.

### Cardiovascular AEs

Cardiovascular AE PTs include the following:

- “Conditions associated with central nervous system haemorrhages and cerebrovascular Accidents” SMQ: Narrow PTs
- “Ischaemic central nervous system vascular conditions” SMQ: Narrow PTs
- “Embolic and thrombotic events, arterial” SMQ: peripheral arterial occlusive disease; peripheral arterial reocclusion; peripheral artery angioplasty; peripheral artery bypass; peripheral artery occlusion; peripheral artery stent insertion; peripheral artery thrombosis
- “Ischaemic colitis” SMQ: Narrow PTs
- “Ischaemic heart disease” SMQ
  - “Myocardial infarction” SMQ: Narrow PTs
  - “Other ischaemic heart disease” SMQ: Narrow PTs

### Suicidality AEs

Suicidality AE PTs include the following:

- “Suicide/self-injury” SMQ: All PTs.

### Local Irritation AEs

Local irritation AE PTs include any of the following:

- “Administrative site reactions NEC” high level term (HLT): PTs in [Table 5 \(Appendix 3.2\)](#) based on clinical review. NEC=not elsewhere classified.
- “Upper respiratory tract signs and symptoms” HLT: PTs in [Table 6 \(Appendix 3.2\)](#) based on clinical review.
- Dysgeusia.

### Hypertension AEs

Hypertension AE PTs include the following:

- “Hypertension” SMQ: Narrow PTs

These AEs will also be summarized for the subgroup of participants with medical history of hypertension.

### Raynaud’s Phenomenon AEs

- AEs with the PT of Raynaud’s phenomenon are included.

#### **6.6.1.4. TEAEs Leading to Discontinuation of Study**

All-cause and treatment-related TEAEs leading to discontinuation of study will be summarized by treatment group.

#### **6.6.2. Laboratory Data**

Laboratory test results will be graded according to numeric laboratory test criteria in Common Terminology Criteria for Adverse Events (CTCAE) if available; otherwise according to Division of Acquired Immune Deficiency Syndrome (DAIDS) Table for Grading the Intensity of Adult and Pediatric Adverse Events. See ([Appendix 4](#)) for details about toxicity grading. Laboratory test groups of clinical interest will include hematology, chemistry, and urinalysis.

Values and changes from baseline in laboratory tests are tabulated as continuous variables at Baseline and EOT for the treatment analysis period by treatment group for the safety analysis set.

Estimated glomerular filtration rate (eGFR) will be calculated using the CKD-EPI equations as defined in Appendix 10.6 of study protocol v1.0 and the lower limit of normal (LLN) is set to 90 mL/min/1.73m^2.

##### **6.6.2.1. Laboratory Test Abnormalities**

Laboratory test abnormalities are summarized as the number and percentages of participants in the safety analysis set in the following frequency tables:

- Worst (highest) on-treatment laboratory test abnormality for each graded laboratory test.

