#### **Medical Conditions:**

1. History of retinal migraine, basilar migraine or hemiplegic migraine.
2. History or current evidence of uncontrolled, unstable or recently diagnosed cardiovascular or cardiometabolic disease including:
  - Diagnosis of ischemic heart disease, coronary artery vasospasm, and cerebral ischemia during the 6 months prior to Screening Visit.
  - Events of MI, ACS, PCI, cardiac surgery, stroke or TIA during the 6 months prior to Screening Visit.

- ECG findings at the Screening Visit including:
    - QTcF interval >470 msec.
    - Left Bundle Branch Block.
    - Right Bundle Branch Block with a QRS duration  $\geq 150$  msec.
    - Intraventricular Conduction Defect with a QRS duration  $\geq 150$  msec.
  - Uncontrolled hypertension (high blood pressure); a single blood pressure measurement of greater than 150 mmHg systolic or 100 mmHg diastolic after 10 minutes of rest at the Screening Visit is exclusionary.
  - Uncontrolled diabetes, defined as HbA1c  $\geq 7.5\%$  at the Screening Visit.
3. Major depressive disorder, anxiety disorder, or other significant psychiatric disorder including:
- Major depressive episode within the last 12 months, major depressive disorder or any anxiety disorder requiring more than 1 medication for each disorder. Medications to treat major depressive disorder or an anxiety disorder must have been at a stable dose for at least 3 months prior to the Screening Visit provided the medication is not otherwise prohibited.
  - Current diagnosis of major depressive disorder requiring treatment with atypical antipsychotics.
  - Schizophrenia, bipolar disorder, or borderline personality disorder.
  - Response of “yes” to Question 4 or 5 for suicidal ideation, **or** on any suicidal behavioral question on the C-SSRS for the period of 1 year prior to Screening Visit and during the study, **or** participants present a serious risk of suicide in the opinion of the investigator (see Section 8.3.7).
4. Acute or chronic pain syndromes (such as fibromyalgia, chronic pelvic pain, CRPS). Other pain syndromes (including trigeminal neuralgia), psychiatric conditions, dementia, or significant neurological disorders (other than migraine) that, in the investigator’s opinion, interfere with study assessments.
5. Conditions that may affect the administration or absorption of the nasal product:
- History of nasal surgery in the 6 months preceding the Screening Visit.

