  - Evidence at Screening Visit of significant nasal conditions (eg, severe septum deviation, nasal deformity or blockage, inflammation, perforation, mucosal

erosion or ulceration, polyposis, nasal trauma) as evaluated by the investigator or medically qualified delegate.

- Presence of piercings in the nose that, in the opinion of the investigator, would be likely to interfere with positioning of the unidose nasal spray device and successful completion of the dosing procedure.
6. History of, treatment for, or evidence of, alcohol or drug abuse within the past 12 months or participants who have met DSM-V criteria for any significant substance use disorder within the past 12 months from the date of the Screening Visit, **or** a positive drug screen for drugs of abuse that in the investigator's judgment is medically significant, in that it would impact the safety of the participant or the interpretation of the study results. In addition:
- Detectable levels of cocaine, amphetamine, and PCP in the drug screen are exclusionary. Participants who are positive for amphetamines, and who are on a prescribed amphetamine medication for an approved indication (ie, ADHD) will be allowed into the study at the investigator's discretion. This determination by the investigator must be well documented in the participant's source medical records. The stimulant dose must be stable from 3 months prior to the Baseline Visit and through the EOT Visit.
  - Detectable levels of marijuana in the drug screen are not exclusionary, if in the investigator's documented opinion the participant does not meet DSM-V criteria for substance use disorder, and the positive test does not signal a clinical condition that would impact the safety of the participant or interpretation of the study results.
7. Hematologic or solid malignancy diagnosis within 5 years prior to the Screening Visit. Participants with a history of localized basal cell or squamous cell skin cancer are eligible for the study if they are cancer-free prior to the Screening Visit in this study.
8. Other social, medical (including drug or other allergy), or psychiatric condition including recent (within the past year) or active suicidal ideation/behavior or laboratory abnormality that may increase the risk of study participation or, in the investigator's judgment, make the participant inappropriate for the study.

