**Diagnostic Assessments:**

13. **ANY** of the following findings at the Screening Visit and laboratory tests as assessed by the study-specific laboratory:
  - Class 2 or Class 3 obesity, defined as body mass index  $\geq 35$  kg/m^2.
  - eGFR  $< 30$  mL/min using the recommended CKD-EPI equations in Section 10.6.2.
  - Total bilirubin  $> 1.5 \times$  ULN (may be repeated once, with fractionation, for confirmation during the Screening Phase, and direct bilirubin  $> 1.5 \times$  ULN is exclusionary if Gilbert's syndrome is suspected).
  - AST (SGOT) or ALT (SGPT)  $> 1.5 \times$  ULN (may be repeated once for confirmation during the Screening Phase).
  - Neutrophil count  $\leq 1000/\mu\text{L}$  (or equivalent).

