### **9.3.5. Safety Analyses**

The frequencies of the following postdose safety endpoints will be tabulated by treatment group for the safety analysis set: AEs by intensity; SAEs; AEs related to study intervention; local irritation AEs; laboratory test abnormalities by toxicity grade; and liver function test elevations.

The investigators will determine the intensity of AEs and the relationship of AEs to study intervention. The investigators' terms will be coded using the latest version of the MedDRA available at the start of the study. AEs will be presented by system organ class and preferred term.

Laboratory test results will be graded according to numeric laboratory test criteria in CTCAE if available; otherwise, results will be graded according to numeric laboratory test criteria in DAIDS Table for Grading the Severity of Adult and Pediatric Adverse Events.

Deaths will be listed without regard to onset for the enrolled analysis set.

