##### 3.2.2. Other Secondary Endpoints

- Percentage of participants with phonophobia absent at 2 hours postdose, evaluated for participants with phonophobia present at the time of dosing.
- Percentage of participants with photophobia absent at 2 hours postdose, evaluated for participants with photophobia present at the time of dosing.
- Percentage of participants with nausea absent at 2 hours postdose, evaluated for participants with nausea present at the time of dosing.

- Percentage of participants with a pain intensity of none at all time points from 2 to 24 hours postdose (sustained pain freedom).
- Percentage of participants with a pain intensity of none at all time points from 2 to 48 hours postdose (sustained pain freedom).
- Percentage of participants with pain relapse (any pain intensity above ‘none’) at any time point after 2 hours postdose, evaluated for participant with pain freedom at 2 hours postdose.
- Percentage of participants taking rescue medication within 24 hours postdose.
- Percentage of participants with a pain intensity of none or mild (pain relief) at 60 minutes postdose.
- Percentage of participants with a functional disability level of normal at 15 minutes postdose, evaluated for participants with functional disability at the time of dosing.
- Number and percentage of participants with AEs of moderate or severe intensity, SAEs, local irritation AEs, and grade 3 or 4 laboratory test abnormalities.

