#### 6.6.4. Electrocardiograms

Values and changes from baseline in ECG parameters will be summarized as continuous variables by treatment group at Baseline and EOT of the on-treatment safety analysis period for the safety analysis set. Results for overall are only shown at Baseline.

ECG abnormalities during on-treatment period will be summarized by treatment group as the number and percentage of participants in the following categories:

- QTcF (msec): > 450 to 480, > 480 to 500, > 500.
- QTcF interval increase from baseline (msec): > 30 to 60, >60.

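### For laboratory tests graded on fixed cut-offs, a grade 3 or 4 value already present at entry counts in the secondary safety endpoint, and no planned table separates it from a new one

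*SAP*

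**What the plan says.** **Endpoint.** The safety item in SAP 3.2.2 ends with "local irritation AEs, and grade 3 or 4 laboratory test abnormalities", and Protocol Section 3 has the same item. Protocol 9.3.5 asks for postdose frequencies that include "laboratory test abnormalities by toxicity grade; and liver function test elevations". Neither requires the abnormality to be new or worse than baseline.

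**Tabulation.** SAP 6.6.2.1 lists a single table: "Worst (highest) on-treatment laboratory test abnormality for each graded laboratory test". Under SAP 3.5.2, laboratory tests are scheduled at Screening and at the EOT or Early Discontinuation visit, and baseline is the last value up to dosing.

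**Entry limits.** Exclusion 13 (Protocol 5.2) applies to "findings at the Screening Visit and laboratory tests as assessed by the study-specific laboratory". Among graded tests it sets numeric limits on eGFR, total bilirubin, AST, ALT and neutrophils. Exclusion 2 rules out "Uncontrolled diabetes, defined as HbA1c" of 7.5% or more. Exclusion 8 allows exclusion for a "laboratory abnormality that may increase the risk of study participation", with no numeric threshold.

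**Other displays.** SAP 6.6.2 summarizes laboratory values and changes from baseline as continuous variables. SAP 6.6.2.2 tabulates liver test elevations for the pre-treatment period as well as on treatment. The current SAP has no table of baseline grade against on-treatment grade.

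**The concern.** A safety reader takes an on-treatment grade 3 or 4 count as something that arose after the dose. For tests graded on absolute values, the planned table cannot support that reading, because a long-standing anemia or proteinuria scores the same as a new one. The SAP holds adverse events to a different standard: under SAP 6.6.1.2.2 an event is treatment-emergent only if it started after dosing. The laboratory part of the same endpoint item has no equivalent rule.

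This matters more in a single-dose study with one scheduled postdose sample, because grade 3 or 4 counts are likely to be small. A few carried-over results can then form a visible share of the total, raising the reported percentages and pulling the ratio between groups toward 1.

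**Working it through.** The plan states no figure for this endpoint, so there is nothing to reproduce. The check compares the grading rules with the entry criteria and then gives an illustration on assumed rates.

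**Step 1: which rows are exposed.**

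- SAP Table 7 has 33 rows. Eosinophils, bicarbonate and LDH have no grade 3 or 4, which leaves 33 − 3 = 30.
- Of these 30, 23 are in the routine panel of Protocol Appendix 2 (Table 2).
- Five of the 23 have a numeric entry limit: ALT, AST, total bilirubin, neutrophils and eGFR.
- Four of the 23 are graded as multiples of baseline when baseline is above ULN: ALT, AST, total bilirubin and ALP. Together with the five above, this makes 6 distinct rows.
- The remaining 23 − 6 = 17 rows (74%) have neither protection: hemoglobin; lymphocytes high and low; platelets; white cells; calcium high and low; CK; creatinine (its ULN-based branch); glucose high fasting, high nonfasting and low; potassium high and low; sodium high and low; urine protein.
- If the eGFR limit is taken to cover creatinine, and the HbA1c limit to cover the two high-glucose rows, 17 − 3 = 14 rows (61%) remain.

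**Step 2: the rule applied to an unchanged value.**

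- Hemoglobin below 8.0 g/dL at Screening and at EOT is grade 3 both times. It is counted as on-treatment grade 3. The same holds for lymphocytes below 500/mm³, CK above 5 × ULN and urine protein 3+.
- ALT between ULN and 1.5 × ULN at Screening and the same at EOT is 1.0 × baseline, below the 1.5 × baseline needed for grade 1. It is grade 0 and is not counted.

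**Step 3: can another table separate the two?** Continuous summaries do not identify the participants counted. The pre-treatment categorical table covers liver tests only, and most of those already have an entry limit or baseline-relative grading.

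**Step 4: illustration on assumed rates.** Suppose new-onset grade 3 or 4 rates of 0.5% on placebo and 1.5% on zavegepant. Let p be the proportion entering with a grade 3 or 4 value, all persisting at EOT. Take 630 per group (the evaluable number in Protocol 9.5, standing in for treated participants). The observed rate is p + (1 − p) × 0.005 on placebo and p + (1 − p) × 0.015 on zavegepant.

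| p (assumed) | Carried over per group | Placebo | Zavegepant | Difference | Ratio | Carried-over share, zavegepant | Power, if tested at 0.05 |
|---|---|---|---|---|---|---|---|
| 0 | 0 | 0.50% | 1.50% | 1.00 points | 3.00 | 0% | 43% |
| 0.5% | 3 | 1.00% | 1.99% | 0.99 | 2.00 | 25% | 31% |
| 1% | 6 | 1.50% | 2.48% | 0.99 | 1.66 | 40% | 24% |
| 2% | 13 | 2.49% | 3.47% | 0.98 | 1.39 | 58% | 17% |
| 3% | 19 | 3.48% | 4.45% | 0.97 | 1.28 | 67% | 14% |

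The risk difference hardly moves, while the ratio and the precision do. No test of this endpoint is planned, so the power column serves only as a measure of noise. The illustration pools all tests. SAP 6.6.2.1 reports test by test, so the effect on any one line would be smaller.

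**The case against.** **The protocol defines the endpoint this way.** Neither the endpoint nor Protocol 9.3.5 has a treatment-emergent condition, and the SAP follows them. This stands, and it is a reason to add a count rather than redefine the endpoint.

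**Entry is not unrestricted.** Exclusion 8 could keep out a participant with marked anemia or a very high CK, and HbA1c and eGFR limit glucose and creatinine indirectly. This stands in part. Exclusion 8 rests on risk or judgment, so the accurate statement is that no numeric limit exists for these tests.

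**Some baseline context exists.** Changes from baseline are summarized, and clinically significant laboratory changes must be recorded as AEs (Protocol 8.3.5), where the treatment-emergent rule applies. This helps, but it does not make the grade 3 or 4 count itself interpretable.

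Four stronger readings are tempting, and the documents do not support them.

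- *A reader might infer that grading ignores baseline for every test.* It does not for ALT, AST, ALP and total bilirubin when baseline is raised, and creatinine also has a baseline-multiple branch.
- *A reader might infer that most on-treatment grade 3 or 4 results would be carried over.* The documents give neither prevalence at entry nor a new-onset rate. In the table above the share runs from 25% to 67% purely according to the assumed p.
- *A reader might infer a bias between groups.* Randomization balances carriers in expectation. What remains is dilution and chance imbalance, in an endpoint with no planned test.
- *A reader might extend the point to QTcF and blood pressure.* Entry excludes "QTcF interval >470 msec", while SAP 6.6.4 tabulates "QTcF (msec): > 450 to 480, > 480 to 500, > 500", so only the lowest category overlaps with an eligible Screening value. The hypertension-history subgroup in SAP 6.6.3 has a similar overlap: systolic above 140 and diastolic above 90 are tabulated, and entry is allowed to 150/100. Both sections also tabulate categories of change from baseline, which largely deals with this, and neither measure belongs to the laboratory endpoint.

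**Conclusion.** The point holds for tests graded in SAP Table 7 on absolute cut-offs and without a numeric entry limit: 17 of the 23 routinely measured rows that can reach grade 3 or 4, or 14 if creatinine and high glucose are treated as indirectly limited. For these, a grade 3 or 4 value present at entry and unchanged at EOT enters the secondary safety endpoint, and no planned table separates it from a new abnormality. The consequence is possible inflation of the absolute percentages and a diluted or noisier contrast, without systematic bias between groups. The row counts follow from the documents. The size of the effect does not, and the illustration rests entirely on its assumed rates and on full persistence to EOT. This is a minor reporting weakness that is cheap to repair.

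**What to change.** In SAP 6.6.2.1, keep the table of worst on-treatment grade and add one of the following:

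- by treatment group, the number and percentage of participants with an on-treatment grade 3 or 4 that is worse than the baseline grade, with baseline as in SAP 3.5.2 and a missing baseline taken as grade 0; or
- for each graded test, a table of baseline grade by worst on-treatment grade.

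State that the baseline value is graded by the same Table 7 rules. The protocol endpoint is unchanged.

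**Cost.** One more table from data already collected, with no change to trial conduct.

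**Downside.** The scheduled baseline sample is taken at Screening, up to 28 days before randomization, and dosing may follow up to 45 days later. It can therefore precede dosing by up to about 28 + 45 = 73 days. A transient abnormality at Screening could then mask a new one on treatment, which is why the existing table should stay alongside.

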### 6.6.2.2. Liver Function Test (LFT) Elevations

#### LFT Elevations: Cumulative, Mutually Exclusive, and Composite

The number and percentage of participants with LFT elevations will be summarized for the safety analysis set for pre-treatment period and on-treatment analysis periods, respectively. LFT elevations are based on fold changes above ULN.

LFT elevations include the following categories:

- Cumulative elevations:
  - ALT > 1 x, > 3 x, > 5 x, > 10 x, and > 20 x ULN
  - AST > 1 x, > 3 x, > 5 x, > 10 x, and > 20 x ULN
  - ALT or AST > 1 x, > 3 x, > 5 x, > 10 x, and > 20 x ULN
  - TBL > 1 x, > 1.5 x, and > 2 x ULN
  - ALP > 1 x, > 1.5 x, and > 2 x ULN
- Mutually exclusive elevations:
  - ALT > ULN to  $\leq 3$  x ULN, > 3 x ULN to  $\leq 5$  x ULN, > 5 x ULN to  $\leq 10$  x ULN, > 10 x ULN to  $\leq 20$  x ULN, and > 20 x ULN
  - AST > ULN to  $\leq 3$  x ULN, > 3 x ULN to  $\leq 5$  x ULN, > 5 x ULN to  $\leq 10$  x ULN, > 10 x ULN to  $\leq 20$  x ULN, and > 20 x ULN
  - ALT or AST > ULN to  $\leq 3$  x ULN, > 3 x ULN to  $\leq 5$  x ULN, > 5 x ULN to  $\leq 10$  x ULN, > 10 x ULN to  $\leq 20$  x ULN, and > 20 x ULN
  - TBL > ULN to  $\leq 1.5$  x ULN, > 1.5 x ULN to  $\leq 2$  x ULN, and > 2 x ULN
  - ALP > ULN to  $\leq 1.5$  x ULN, > 1.5 x ULN to  $\leq 2$  x ULN, and > 2 x ULN
- Composite elevations:
  - ALT or AST > 3 x ULN and TBL > 1.5 x ULN
  - ALT or AST > 3 x ULN and TBL > 2 x ULN
  - ALT or AST > 3 x ULN concurrent with TBL > 2 x ULN. Concurrent is defined as elevations on the same collection date.
  - ALT or AST > 3 x ULN concurrent with TBL > 2 x ULN and ALP  $\leq 2$  x ULN. Concurrent is defined as elevations on the same collection date.

- ALT or AST > 3 x ULN concurrent with a selected AE:
  - The following PTs are used to identify selected AEs: nausea, vomiting, decreased appetite, fatigue, and those containing “abdominal pain”.
  - Results are also displayed for each selected AE
  - For a given safety analysis period, an LFT elevation is concurrent with an AE of interest if the imputed AE start date is +/- 7 days inclusive of the LFT collection date; both the LFT collection date and the imputed AE start date must also be in the safety analysis period.

